**Last Updated: 06/04/2014**

**NCT: Not available**

## Detailed Protocol

### Successful Aging and Enrichment (SAGE): Effects of Environmental Stimulation on Cognitive Health and Neural Plasticity

#### Background and Significance

Increasing numbers of individuals are living into old age [1-3]. According to a recent UN report (2007), individuals over the age of 60 are the fastest growing age group on earth. They currently account for 700 million people around the world. By 2050, the numbers are expected to grow to 2 billion. The number of individuals projected to become demented is proportional to the growth in the aging population. Today around 25 million people suffer from dementia, a disease that is relatively rare before the age of 65. After 65, the proportion of demented persons in the population doubles every five years until 90+, when approximately half of that population suffers from this syndrome. The global cost of dementia care in 2009 has been estimated to \$421.6 billion [4]. If nothing can be done to prevent, cure, or at least delay the incidence of dementia, the resources to take care of all demented individuals will constitute an enormous burden for many countries. Advancing our knowledge about factors that contribute to cognitive health among the elderly is thus both an important and urgent task. Models developed by Brookmeyer and colleagues [5] suggest that an intervention that could delay the mean onset of Alzheimer's Disease (AD) by ~5 years would lead to a 50% reduction in incident rates. Even a 1 year delay would be associated with a 10% reduction in incidence.

A large number of epidemiological studies have found that an active lifestyle contributes to cognitive health across the lifespan [6]. The protective factors reported include intellectual and physical enrichment activities; social activities and networks; awareness and concentration (mindfulness) practices; and cognitive activity. Some studies have indicated that these types of activities may also have a positive effect when performed late in life. Critics, however, claim that associations from epidemiological studies do not constitute a sound basis for conclusions about causality.

In 2010, a systematic review of potential factors that might prevent cognitive decline indicated that the quality of evidence was low for all reported factors, except for cognitive training, the main reason being lack of experimental validation in human studies [7]. More recently, one experimental study in humans found that physical exercise had positive effects on BDNF, an important marker of neural plasticity and cognitive health [8].

A common model to explain the possible effect of environmental stimulation on cognitive health involves its impact on reserve capacity [6, 9]. The basic idea is that a brain that has received more stimulation will have richer neural networks and greater capacity to develop new neural connections with learning (i.e., the stimulated brain will be more plastic). Another implication is that loss of function of part of a brain (e.g., due to underlying neurodegenerative disease, stroke, or trauma) can more easily be compensated for. On a cognitive level, reserve could also facilitate the development of alternative processing strategies or behaviors to compensate for difficulties in a particular area.

The evidence that physical stimulation, mental stimulation, and awareness (mindfulness) training may have beneficial effects on the brain and cognition is reviewed below.

Detailed Protocol: SAGE

### **Physical Activity**

Studies of animals have indicated that exercise promotes neurogenesis and synaptogenesis. Exercise up-regulates the production of brain derived neurotrophic factor (BDNF) [10, 11]. BDNF is believed to help induce neurogenesis and promote survival and/or neuronal differentiation. It has also been linked to long-term potentiation necessary for memory formation. A Cochrane Database System Review [12] noted that 8 out of 11 randomized controlled exercise intervention studies reported that structured aerobic exercise interventions resulted in increased cardiorespiratory fitness of the intervention group, with an average improvement of approximately 14%. This improvement was associated with better performance on cognitive functions, including auditory attention (effect size 0.52), speed of information processing (effect size 0.26), and visual attention (effect size 0.26).

Physical activity and exercise has been associated with the enhancement of cognitive and brain function, and with a reduced risk for clinical dementia [13-22]. A recent review article published in *Nature Reviews: Neuroscience* [23] concluded that physical activity improved cognition in both normal older adults and patients with early AD. Although benefits were seen for a range of cognitive functions, there appeared to be disproportionate improvement in executive control (including planning, working memory, and multi-tasking). Particularly intriguing are the exercise intervention studies that have looked at effects on not only cognition but also underlying brain structure and activity. For instance, in a study reported by Colcombe and colleagues [24], older individuals who participated in an aerobic training group exhibited significant increases in the size of components of the prefrontal cortex and superior temporal lobes. In another study by the same researchers [25], more physically fit older subjects as well as those randomly assigned to participate in the aerobic fitness training group performed better on an attention task (more efficient response to conflicting cues on a flanker task). Moreover, functional magnetic resonance imaging (fMRI) revealed that older subjects exhibited greater neural activity in regions associated with attentional control (middle and superior frontal gyrus, superior parietal lobule) and less activity in the anterior cingulate cortex.

### **Cognitive Stimulation**

There have been numerous studies comparing animals placed in “enriched” versus standard environments. An enriched environment often means a cage filled with potentially interesting objects and structures to explore. The opportunity for aging animals to interact with a more complex environment appears to influence neurogenesis, dendritic complexity, the capacity to compensate for injury, and promotes cognitive abilities and the capacity to compensate for injury [26-30].

Morphometric MRI studies of the human brain have provided evidence that cognitive activity or training alters brain morphology of relevant structures, leading to an increase in cortical thickness. For example, comparisons of the MRIs of individuals learning to juggle versus those of control subjects reveal an increased size of bilateral mid-temporal grey matter and left posterior intra-parietal sulcus, structures associated with the visual processing of movement [31]. Similarly, comparisons of the MRIs of licensed London taxi drivers versus control subjects reveal increased volume of the posterior hippocampus believed to help mediate spatial memory [32]. fMRI has been used to examine the impact of cognitive training on older adults. For example, Erickson and colleagues [33] conducted a randomized, longitudinal dual-task training study in older subjects. They found that training improved task performance and was associated with an increase in asymmetric hemispheric activation (increase in left and decrease in right hemisphere activity within the ventral lateral prefrontal cortex (PFC), and a

## Detailed Protocol: SAGE

decrease in age-related differences in the pattern of prefrontal activation). Logan and colleagues [34] found that training that emphasized semantic elaboration during a memory encoding task led to improved performance of older subjects. This was associated with increased activity of the PFC (especially the left ventral region), which, compared to young subjects, had been under-recruited at baseline, prior to training. Both studies suggest that the aging brain can exhibit plasticity that may be influenced by training and intervention programs.

Formal cognitive training has been shown to improve measures of intellectual performance. For example, in a study by Ball and colleagues [35], older individuals (65-94 years old) were randomly assigned to one of three training groups for memory (verbal episodic memory), reasoning (problem-solving that follows a serial pattern), or speed of processing (visual search and identification), or to a control group. The initial intervention improved performance relative to baseline; however the improvement was limited to the cognitive realm that had been targeted. Improvements lasted through the 2 years of follow-up. Other studies also have supported the potential benefit of cognitive training in older adults [22, 36, 37]. Recently, there has been some evidence of transfer of improvement beyond the specific cognitive activity that was trained, especially when the training was directed at working memory and executive control [38-40].

### **Mindfulness Meditation**

The literature indicates that there are two types of mindfulness. Each is comprised of pragmatic practices and psychological orientations. In relation to both types of mindfulness, Jon Kabat-Zinn refers to the pragmatic aspects of mindfulness as a “scaffolding” used to support the psychological orientations of mindfulness [41].

The first type of mindfulness is derived from ancient contemplative traditions (e.g., Buddhist meditation practices) [42]. Pragmatically, this first type can include the practice of taking a seated posture with the eyes closed or partially open, the practice of walking, or another pedestrian task, while silently focusing on observing somatic sensation, sensory stimuli (sound, smell), breath, mental activity, or emotional activity [43, 44]. The psychological orientation during this pragmatic practice is described by Kabat-Zinn as “paying attention in a particular way: on purpose, in the present moment, and non-judgmentally to the unfolding of experience moment to moment” [45]. There is no attempt to alter perception, just to direct attention .

The second type of mindfulness has been pioneered by Ellen Langer and is concerned with shifting perspective, or “reperceiving” [46]. The pragmatic practice for this type of mindfulness is outward focused: one observes a person, thing, or idea. Psychologically, one is still oriented to non-judgment and moment-to-moment awareness, but, in addition, one is oriented to experience the person, place, or idea in novel ways [47].

There are several other integral components of psychological orientation in both forms of mindfulness. One is non-striving: instead of choosing a goal-oriented or competitive mindset, one cultivates an attitude of patience, compassion, and acceptance for what is happening in the present moment. Also, instead of a discriminating mindset, one chooses a mindset of inclusive curiosity [46]. Instead of seeking to avoid unpleasant experience or retain pleasant experiences, all experiences are seen as equally valuable [48]. We aim to include aspects of all of these components and practices in our mindfulness intervention.

Detailed Protocol: SAGE

There is evidence of the impact of mindfulness practice on attentional control and mental efficiency [49-54]. Both intervention and comparison studies of long-term meditators vs. non-meditators suggest that mindful meditation may alter brain structure and physiology [49-51, 55-61]. The literature also supports the feasibility of mindfulness training in older adults [62, 63].

To the best of our knowledge, the proposed study would be the first to experimentally compare the impact of different types of structured training programs on markers of cognitive and brain health in older adults.

### **Relevant Previous Research by the Project's Investigators**

The proposed research is a collaborative effort between Linnaeus University, Vaxjo, Sweden and the Brigham and Women's Hospital, Boston MA. It brings together researchers who have been investigating different aspects of cognitive aging.

The proposed studies parallel on-going research at Sweden's Karolinska Institutet Alzheimer's Disease Research Center (KI-ADRC), headed by [name]. [name] and [name] have previously cooperated on studies concerning the role of BDNF on cognitive function in older animals. Their previous findings from experimental studies on rats showed that environmental stimuli can have a positive impact on brain anatomy, behavior, and learning ability [64-66]. Environmental stimulation increased levels of BDNF [65, 67] in the hippocampus and cortex, two brain regions critically involved in cognitive functioning. Environmentally induced elevation of BDNF levels in experimental animals was related to enhanced spatial learning [66, 68]. It is unclear whether environmental stimulation in humans modifies neurotrophin levels or cognitive functioning. In humans, various types of stimulation are being considered as prime candidates (e.g., physical exercise and [69] cognitive stimulation [70]). However, which type of stimulation is most effective and whether the effects can be observed in elderly persons is unknown.

[name] has reported that people with higher education are less likely to suffer from dementia [71], which has been interpreted as resulting from long-term intellectual stimulation. Moreover, such findings are consistent with the model of "cognitive reserve", which holds that capacities, in particular brain-involved capacities, that developed over time serve to mitigate negative effects of age- and disease-related changes in the brain. It was also found that individuals who had been living with another person as part of a relationship had lower risk of dementia in later life [72], which can be interpreted as a result of social and perhaps even intellectual stimulation. However, since both of these results come from epidemiological studies, we cannot ascertain a causal link with cognitive health. Even less can be said about possible functional factors behind this association. For example, is the cognitive health benefit associated with a long-term relationship due to the intellectual challenges of taking into account the views and needs of a partner? Or is the cognitive benefit due to the social/emotional consequences of living with someone?

The Laboratory of Healthy Cognitive Aging at BWH under the direction of [name] has investigated curiosity (attention to the novel aspects of one's environment) and cognitive reserve in normal aging and neurological disease [73-82]. His lab has demonstrated that successful cognitive aging is strongly associated with increased engagement by novel stimuli, as measured by electrophysiological (event-related potentials) and behavioral markers [74]. The difference between high and average cognitive performers in attention to novelty increases with age [74]. However, even among cognitively successful

## Detailed Protocol: SAGE

older adults (individuals in their upper 80s and 90s), cognitive resources may be insufficient to compensate for age-associated neural changes [81]. Greenwood and Parasuraman have argued that exposure to novelty, requiring the brain to adapt to changing demands, serves as a key factor in promoting brain plasticity and cognitive integrity [83].

If interest in novelty is both a marker and promoter of cognitive health, it is critical to determine if this process can be influenced through structured interventions involving cognitively stimulating activities, physical exercise, or mindfulness training. To our knowledge, the proposed study would be the first to systematically test this possibility.

Finally, work at BWH by [name] has utilized transcranial doppler (TCD) studies to examine cerebral blood flow responses in healthy older adults [84-86]. TCD can determine the extent to which subjects are capable of enhancing cerebral blood flow in response to cognitive demands and whether these responses can be altered by experimental interventions. Neurovascular coupling reflects the link between regional synaptic activity and regional cerebral blood flow. Under normal conditions, cerebral blood flow and cerebral metabolic rate are coupled, with an increase in metabolic demand leading to an increase in blood flow. [name] lab has shown that compared to fast walking elders, those who are slow walkers exhibit impaired neurovascular coupling [84]. Another study demonstrated that the pattern of blood flow velocities in anterior and posterior circulations differ between healthy old and young subjects [85]. A recently published report indicated a strong link between neurovascular coupling and cognitive performance in older adults. In individuals with baseline impairments, there was improvement in neurovascular coupling and cognitive function with regular cocoa consumption, which may be due to its antioxidant, anti-inflammatory, or cholinergic properties [86].

In summary, the current project engages experts from major research institutions that represent different perspectives (biological, pharmacological, psychological, clinical and epidemiological) and who bring experience using different methodological approaches. The composition of this research team should facilitate an interdisciplinary approach to study factors of importance for maintaining brain health in later life. Together, we have published over 1,000 articles in the field.

### **Specific Aims**

The overarching goal of the current study is to identify factors that promote neural plasticity and cognitive health in elderly persons.

The specific aims address the impact of different types of structured mental or physical stimulation over a 5 week training period on the following:

1. Biological markers of brain plasticity (e.g., BDNF)
2. Electrophysiologic markers (event-related potentials) of neural efficiency and capacity
3. Neuropsychological markers of cognitive performance
4. Vascular markers of cerebral health (e.g., neurovascular coupling using transcranial doppler)

### **Subject Selection**

We aim to have 200 subjects complete the study. There are two sites: one at BWH and one at Linnaeus University, Vaxjo, Sweden, with 100 subjects participating at each site.

## Detailed Protocol: SAGE

Subjects will be recruited at the two sites with the aim of obtaining a representative sample of healthy, elderly participants 65 and older in each country. At BWH, subjects will be recruited through several channels, including announcements in local newspapers and other available media; outreach to independent living communities; senior activity centers and organizations; and through existing databases for studies of healthy aging that exist at BWH.

To be included in the study, participants must:

1. Be 65 or older
2. Have  $\geq 8$  years of education
3. Be sufficiently fluent in the English language to understand instructions and perform the neuropsychological tests (as the purpose of the project is to study healthy aging)
4. Score above levels indicating possible cognitive impairment on the Mini Mental State Exam (MMSE) ( $\geq 26$ ) [87]
5. Have an estimated intelligence quotient (IQ) score  $\geq 90$  based on the American National Reading Test (AmNART) [88]
6. Have a score within 2 SD of the age-appropriate mean on the short form of the Boston Naming Test [89, 90]
7. Have a score within 2 SD of the age-appropriate mean on the Logical Memory Subtest of the Wechsler Memory Scale—Third Edition [91]

Subjects will be excluded for any of the following reasons:

1. History of CNS diseases or major psychiatric disorders based on DSM-IV criteria [92]
2. Score of  $> 10$  on the Geriatric Depression Scale [93]
3. Corrected visual acuity worse than 20-50 as tested by a Snellen wall chart
4. Severe hearing disability that would interfere with their ability to participate in the experiments (e.g., to hear instructions and participate in cognitive testing)
5. Medical conditions (e.g., heart or pulmonary disease) that would prevent them from participating in the physical exercise training program
6. Evidence of substantial functional decline based on interview questions and completion of a questionnaire based on the Clinical Dementia Rating Scale [94] by an informant who knows the subject well

Permission will be obtained from subjects to contact their primary care physicians (PCPs). PCPs will be asked to confirm that if their patient were assigned to the physical training condition, he/she could safely participate. Subjects will be excluded if their PCP does not confirm that they can safely participate.

All subjects meeting the inclusion/exclusion criteria will be entered in the study, regardless of race, ethnic background, or gender. Every effort will be made to actively recruit minorities and women to reflect the racial and gender composition of the age group studied.

We anticipate that subjects will reflect the current demographic composition of the Boston area, with approximately 12% from minority groups. In our prior studies on cognitive aging, ~17% of subjects were from minority populations (~10% of which were African American). Approximately 58% of our subjects

Detailed Protocol: SAGE

have been women (which reflect the demographics of a population of older subjects). We anticipate having a similar mixture of subjects in the proposed study.

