### Screening Evaluation (for inclusion/exclusion)

#### Cognitive Screen

- *The Mini-Mental State Examination (MMSE)*, a broad cognitive test on memory, spatial ability, memory and orientation, commonly used to screen for cognitive impairment [87]
- *American National Adult Reading Test (AmNART)*, a test of word pronunciation that provides an estimated IQ [88]
- Logical Memory I and II, Wechsler Memory Scale—Third Edition, a test of verbal memory [91]
- *Boston Naming Test (Short-form, 15-items)*, a test of confrontation naming [89, 90].

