#### **Biostatistical Analysis**

## Detailed Protocol: SAGE

We will mainly use MANCOVA methods to compare the different conditions while controlling for various background factors, such as age and baseline cognitive performance. Cognitive change scores will be the main outcome variables. In addition, we will analyze changes from baseline in BDNF levels, gait score neural activity, as measured by ERPs, and degree of vascular coupling, as measured by TCDs.

In separate analyses, we will investigate whether various cognitive domains (e.g., executive functions, memory) are differentially affected by different types of stimulation. We will also perform separate analyses for closer investigation of how age, education, intelligence and mood may modify the experimental effects.

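### Do the English-fluency and American reading-test criteria conflict with a half-Swedish sample?

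*Protocol*

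**What the plan says.** All of the wording at issue is in the Protocol; no statistical analysis plan is at hand. Subject Selection states: "There are two sites: one at BWH and one at Linnaeus University, Vaxjo, Sweden, with 100 subjects participating at each site". It then gives the aim of "obtaining a representative sample of healthy, elderly participants 65 and older in each country". One sentence on recruitment channels, marked as applying to the Boston hospital (BWH), follows. After it comes a single list of seven inclusion criteria for the study, with no site label.

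Criterion 3 is: "Be sufficiently fluent in the English language to understand instructions and perform the neuropsychological tests". Criterion 5 sets an estimated IQ of at least 90, "based on the American National Reading Test (AmNART"; the Cognitive Screen section describes that instrument as "a test of word pronunciation that provides an estimated IQ". Criteria 4, 6 and 7 use the MMSE, the short Boston Naming Test and Logical Memory, with no test language given.

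The section goes on: "All subjects meeting the inclusion/exclusion criteria will be entered in the study". The next paragraph says: "We anticipate that subjects will reflect the current demographic composition of the Boston area". Biostatistical Analysis compares the conditions while "controlling for various background factors, such as age and baseline cognitive performance".

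**The concern.** The sampling aim and the criteria stand a few lines apart, and for Vaxjo they do not fit together. A person who must understand English instructions and pronounce English words well enough to reach an IQ cut-off is not a typical healthy older Swede. If the list were applied there as written, half the sample would be filtered on second-language ability, and the aim of representing each country would fail for Sweden.

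If the list is not applied there, the document states no eligibility rule for 100 subjects. The two halves might then be screened for IQ, naming and verbal memory with different tests and cut-offs. That matters more than usual in this trial: cognitive change is the main outcome, baseline cognition is a named covariate, and intelligence is to be studied as an effect modifier. Eligibility also belongs in a protocol, so the point cannot be set aside as a detail for the analysis plan.

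**Working it through.** No formula in the Protocol bears on this point. The only arithmetic is 100 + 100 = 200 and 100/200 = 50%, which confirms that half the sample is Swedish. The rest is a question of what the inclusion list covers.

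**Step 1: what the document describes, place by place.**

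| Protocol section | Place described |
|---|---|
| Subject Selection, recruitment channels | Boston hospital |
| Subject Selection, expected demographics | Boston area |
| Phone Screen | Both assessments, and parking, at the Boston hospital |
| Pre-Intervention Assessment | Boston laboratory |
| Blood Samples | Boston clinical research centre |
| Physical exercise training, data upload | Boston laboratory |
| Post-Intervention Assessment | Boston laboratory, dollar payments, hospital parking vouchers |
| Risks and Discomforts | US emergency number |
| Monitoring and Quality Assurance | US institutional review committee |

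Sweden appears as a collaborating site (Relevant Previous Research), as the source of 100 subjects (Subject Selection) and as the place where the exercise video is being developed. There is no Swedish recruitment channel, visit location, laboratory, payment or ethics committee. The absence of Swedish criteria is therefore part of a general pattern and not an isolated omission.

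**Step 2: does unqualified wording mean both sites?** The Phone Screen text says without qualification that every participant attends the Boston hospital before and after training. If that covered both sites, 100 people enrolled in Vaxjo would cross the Atlantic for two assessments of two half-day sessions each. That cannot be meant. So in this document an unlabelled statement about participants can refer to Boston alone. The expected demographics show the same usage, since a sample that is half Swedish could not mirror Boston.

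**Step 3: what each reading implies.**

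- *Boston only.* No English criterion operates in Sweden and nothing conflicts with the sampling aim. The Swedish rules are simply not in this document.
- *Both sites.* Criteria 3 and 5 narrow the Swedish sample, and the sampling aim fails there.

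**Step 4: effect on the trial's comparison.** Under Randomization, the condition is fixed before the first visit. The screening tests are given at that visit, before any training. Language and reading ability at screening are thus baseline characteristics, and the same rule applies whichever condition was drawn. Applying the criteria in English, in Swedish or with different instruments at the two sites can change who is in the sample, but it does not favour one arm. What could change is the population to which the result generalises.

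**Step 5: can the loss of representativeness be sized?** If a fraction *f* of otherwise eligible older Swedes passed criteria 3 and 5, the share removed would be 1 − *f* and the number screened to enrol 100 would be 100/*f*. The Protocol gives no *f* and nothing from which to derive one. Any figure would restate a guess.

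**The case for a change.** The strongest argument for a change is that the authors did mark site scope when they meant it: the recruitment sentence directly before the list is labelled as Boston's, and the list is not. It is headed as applying to the study, and the next paragraph enters all who meet it. The document presents a two-site study and points to no Swedish annex. On the Boston-only reading, eligibility for half the subjects is still nowhere to be seen.

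Part of this stands. The list has no label, and a label would make the text clearer. But the argument from careful labelling fails on the Phone Screen paragraph, which is equally unlabelled and can only mean Boston. That Swedish criteria are absent from this document also does not show that the Swedish team has none; the document is silent on all of that site's operations.

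The worry about pooling deserves an answer too. Different screening instruments could shift the level of ability between sites, and IQ estimates from two reading tests are not automatically on one scale. That bears on how the secondary modifier analysis by intelligence is scaled. It does not bias the comparison of conditions. The covariate list in Biostatistical Analysis is introduced as examples, so it leaves room for site. Whether site enters the model or the allocation is commonly left to the analysis plan, and it is a separate matter from English fluency.

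**Conclusion.** No change to the plan is needed. The wording is loose: criteria that depend on English carry no site label in a study with 100 of 200 subjects (50%) in Sweden. Read with the rest of the document, the list has Boston scope and the conflict disappears. Criterion 3 also states its own purpose, which is that subjects can follow instructions and take the tests; at Vaxjo, fluency in the language of testing serves that purpose. This is a gap that the Swedish site would fill sensibly, and labelling it would alter no estimate or test.

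The conclusion rests on two assumptions that the Protocol does not spell out: that Vaxjo tests its subjects in Swedish with corresponding criteria, and that eligibility is judged without regard to the allocated condition. If the first were wrong, the cost would be a Swedish sample less typical of its country, of unknown extent, and still no bias between arms.
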